7.0 SUPPORTIVE CARE AND OTHER CONCOMITANT THERAPY

7.1 Concurrent Anticancer Therapy

Concurrent cancer therapy, including chemotherapy, radiation therapy, immunotherapy, or biologic therapy may NOT be administered to patients receiving study drug. If these treatments are administered the patient will be removed from protocol therapy.

7.2 Investigational Agents

No other investigational agents may be given while the patient is on study.

7.3 Supportive Care

Appropriate antibiotics, blood products, antiemetics, fluids, electrolytes and general supportive care are to be used as necessary. See COG Supportive Care Endorsed Guidelines at <https://childrensoncologygroup.org/index.php/cog-supportive-care-endorsed-guidelines> for more information.

7.4 Growth Factors

Growth factors that support platelet or white cell number or function can only be

THIS PROTOCOL IS FOR RESEARCH PURPOSES ONLY, SEE PAGE 1 FOR USAGE POLICY

administered in accordance with [Section 6.1.1.2](#) or for culture proven bacteremia or invasive fungal infection. The Study Chair should be notified before growth factors are initiated.

8.0 EVALUATIONS/MATERIAL AND DATA TO BE ACCESSIONED

8.1 Required Clinical, Laboratory and Disease Evaluation

All clinical and laboratory studies to determine eligibility must be performed within 7 days prior to enrollment unless otherwise indicated. Laboratory values used to assess eligibility (see [Section 4.0](#)) must be no older than seven (7) days at the start of therapy. Laboratory tests need **not** be repeated if therapy starts **within** seven (7) days of obtaining labs to assess eligibility. If a post-enrollment lab value is outside the limits of eligibility, or laboratory values are older than 7 days, then the following laboratory evaluations must be re-checked within 48 hours prior to initiating therapy: CBC with differential, bilirubin, ALT (SGPT) and serum creatinine. If the recheck is outside the limits of eligibility, the patient may not receive protocol therapy and will be considered off protocol therapy. Imaging studies, bone marrow aspirate and/or biopsy, must be obtained within 14 days prior to start of protocol therapy (repeat the tumor imaging if necessary).

STUDIES TO BE OBTAINED	Pre-Study	During Cycle 1	Prior to Subsequent Cycles [^]
History	X	Weekly	X
Physical Exam with vital signs ¹²	X	Weekly	X
Height, weight, BSA	X		X
Performance Status	X		
CBC, differential, platelets	X	Twice Weekly (every 3 to 4 days) ³	Every subsequent cycle on D1 ⁴ and D15 ⁴
Pharmacokinetics ¹	X	X	X
Urinalysis	X		
Electrolytes including Ca ⁺⁺ , PO ₄ , Mg ⁺⁺	X	Weekly	X
Creatinine, ALT, bilirubin	X	Weekly	X
Albumin	X		X
Tumor Disease Evaluation	X	End of Cycle 1	Every other cycle x 2 then q 3 cycles ⁵
Tumor Disease Evaluation- Part B Phase 2	X		After cycles 2,4 and 6 and then q 3 cycles ⁵
Bone Marrow Evaluation ⁷	X	End of Cycle 1 ⁸	Every other cycle x 2 then q 3 cycles ⁸
Pregnancy Test ²	X	With tumor disease	With tumor disease

THIS PROTOCOL IS FOR RESEARCH PURPOSES ONLY, SEE PAGE 1 FOR USAGE POLICY

		evaluation ²	evaluation ²
Oxygen Saturation ⁶	X		
Immunogenicity Study	X	X ⁹	X ⁹
T Lymphocyte Saturation	X	X ¹⁰	X ¹⁰
Total Soluble SEMA4D	X	X ¹¹	X ¹¹
Tumor Tissue	X ¹³	X ¹⁴	X ¹⁴

- [^] Studies may be obtained within 72 hours prior to the start of the subsequent cycle.
- ¹ See [Section 8.3](#) for timing of PK studies.
- ² Women of childbearing potential require a negative pregnancy test prior to starting treatment; sexually active patients must use an acceptable method of birth control for the duration of the study. Abstinence is an acceptable method of birth control. Pregnancy testing is required prior to tumor imaging per institutional guidelines.
- ³ If patients have Grade 4 neutropenia then CBCs should be checked at least every other day until recovery to Grade 3 or until meeting the criteria for dose limiting toxicity.
- ⁴ If patients develop Grade 4 neutropenia then CBCs should be checked every 3 to 4 days until recovery to Grade 3
- ⁵ Tumor Disease Evaluation should be obtained on the next consecutive cycle after initial documentation of either a PR or CR. Subsequent scans may restart 2 cycles after the confirmatory scan. Please note that for solid tumor patients, if the institutional investigator determines that the patient has progressed based on clinical or laboratory evidence, he/she may opt not to confirm this finding radiographically.
- ⁶ Only if there is clinical indication of inadequate pulmonary function. See [Section 4.1.7.4](#).
- ⁷ Patients with known bone marrow disease should have baseline bone marrow evaluation
- ⁸ If bone marrow evaluation pre-study is positive for metastatic disease
- ⁹ Immunogenicity Study see [section 8.4](#) for timing of Immunogenicity studies
- ¹⁰ T Lymphocyte Saturation see [section 8.5](#) for timing of T Lymphocyte Saturation studies
- ¹¹ Total Soluble SEMA4D Solubility Assay see [section 8.6](#) for timing of SEMA4D solubility studies.
- ¹² Monitor vital signs every 15 minutes during VX15/2503 infusion and every 30 minutes thereafter for 4 hours.
- ¹³ Tumor tissue should be obtained if available. If a patient does not have tissue available, the study chair must be notified prior to enrollment. See [Section 8.7](#).
- ¹⁴ In the event a subject requires a biopsy for surgery and tumor tissue is removed, tumor tissue will be requested for analysis. Tumor biopsies will not be performed solely for research purposes. See [Section 8.7](#).

8.2 Radiology Studies

- 8.2.1 Central Radiology Review for Response: Patients who respond (CR, PR) to therapy or have long term stable disease (SD) (≥ 6 cycles) on protocol therapy will be centrally reviewed. COG Operations Center will notify the Imaging Center of any patient requiring central review. The Imaging Center will then request that the treating institution forward the requested images for central review. The central image evaluation results will be entered into RAVE for review by the COG Operations Center and for data analysis.

The images are to be forwarded electronically to the Imaging Research Center at Children's Hospital Los Angeles via the ImageInBox.

COG institutions that are not connected via the ImageInBox can send the images on CD ROM or USB flash drive. Submitted imaging studies should be clearly

THIS PROTOCOL IS FOR RESEARCH PURPOSES ONLY, SEE PAGE 1 FOR USAGE POLICY

marked with the COG patient ID, study number (ADVL1614) and date and shipped to [REDACTED]

[REDACTED]

8.3 Pharmacology (Required)

8.3.1 Description of Studies and Assay

Pharmacokinetics (PK) will be performed to determine the PK of VX15/2503 in children. Serum will be collected and VX15/2503 concentration will be determined by a qualified ELISA assay. Samples will be analyzed by Covance Laboratories.

8.3.2 Sampling Schedule (See [Appendix IV](#) and [Appendix IX](#))

- a. For patients ≤ 10 kg, blood samples will be obtained prior to drug administration and at the following time points:
 - Cycle 1, Day 1: prior to start of infusion [3.5 ml], at the end of infusion [2.5 ml], and 2 hours following the end of infusion [2.5 ml]
 - Cycle 1, Day 15: prior to start of infusion [2.5 ml]
 - Cycle 2, Day 1: prior to start of infusion [3.5 ml]
 - Cycle 2, Day 15: prior to start of infusion [2.5 ml]
 - Each subsequent cycle, Day 1: These samples are collected in conjunction with the immunogenicity study samples for patients ≤ 10 kg. No extra blood draws or sample tubes for PK are required for these time points. See [Section 8.4.2](#) for timing and blood volume.
- b. For patients > 10 kg, blood samples will be obtained prior to drug administration and at the following time points. Blood sample volumes are 2.5 ml unless otherwise indicated:
 - Cycle 1, Day 1: prior to start of infusion, at the end of infusion, and 2 hours following the end of infusion.
 - **Note:** The PK samples collected prior to infusion and at the end of infusion are collected in conjunction with the immunogenicity study samples for patients > 10 kg on Cycle 1 Day 1. No extra blood draws or sample tubes for PK are required for these time points. See [Section 8.4.2](#) for timing and blood volume.
 - Cycle 1, Days 4 (± 1), 8 (± 1)
 - Cycle 1, Day 15: prior to start of infusion and at the end of infusion.
 - Cycle 2, Day 1: prior to start of infusion, at the end of infusion, and 2 hours following the end of infusion.
 - **Note:** The PK sample collected prior to start of infusion is collected in conjunction with the immunogenicity study sample for patients > 10 kg on Cycle 2 Day 1. No

THIS PROTOCOL IS FOR RESEARCH PURPOSES ONLY, SEE PAGE 1 FOR USAGE POLICY

extra blood draws or sample tubes for PK are required for this time point. See [Section 8.4.2](#) for timing and blood volume.

- Cycle 2, Day 15: prior to start of infusion.
- Each subsequent cycle, Day 1: These samples are collected in conjunction with the immunogenicity study samples for patients > 10kg. No extra blood draws or sample tubes for PK are required for these time points. See [Section 8.4.2](#) for timing and blood volume.

8.3.3 Sample Collection and Handling Instructions

Please refer to the lab manual. Briefly, blood samples will be collected in SST tubes at a site distant from the infusion for pharmacokinetic evaluation. Please note above which samples are 2.5 ml and which samples are 3.5 ml. For blood samples that are to be used for both pharmacokinetic analysis and immunogenicity analysis, 3.5 ml of blood will be drawn total for both analyses. See [Section 8.4.2](#) and [Section 8.4.3](#) for details. Samples cannot be drawn from the 2nd lumen of a multi-lumen catheter through which drug is being administered. Record the exact time that the sample is drawn along with the exact time that the drug is administered. Please include the infusion start and stop times.

8.3.4 Sample Processing

Refer to lab manual for sample processing details.

8.3.5 Sample Labeling

Each tube must be labeled with the patient's study registration number, the study I.D., and the date and time the sample was drawn. Data should be recorded on the Pharmacokinetic Study Form (see [Appendix IV](#) and [Appendix IX](#)), which must accompany the sample(s). Additional details will be provided in the Covance lab manual.

8.3.6 Sample Shipping Instructions

Samples should be batched per patient and shipped frozen on dry ice in opaque containers at the end of cycle 1 to the lab processing the samples. Primary and backup samples should not be shipped at the same time, please refer to lab manual for detailed shipping information.

Samples should be shipped to the following address:
Covance Central Laboratory Services, Inc.
[name]
[name]

8.4 **Immunogenicity Study (Required)**

8.4.1 Description of Studies

Serum samples will be evaluated for Anti-Drug Antibodies through a qualified ELISA assay.

8.4.2 Sampling Schedule (See [Appendix V](#) and [Appendix X](#))

THIS PROTOCOL IS FOR RESEARCH PURPOSES ONLY, SEE PAGE 1 FOR USAGE POLICY

- a) For patients ≤ 10 kg, samples will be collected at:
 - Cycle 3, Day 1 and each subsequent cycle, Day 1: prior to start of infusion.
 - o **Note:** 3.5 ml of blood will be drawn and will be used for both the immunogenicity analyses and the pharmacokinetic analyses.
- b) For patients > 10 kg, samples will be collected at:
 - Cycle 1, Day 1: prior to start of infusion and at the end of infusion.
 - o **Note:** 3.5 ml of blood will be drawn and will be used for both the immunogenicity analyses and the pharmacokinetic analyses.
 - Each subsequent cycle, Day 1: prior to start of infusion.
 - o **Note:** 3.5 ml of blood will be drawn and will be used for both the immunogenicity analyses and the pharmacokinetic analyses.

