APPENDIX II: CORRELATIVE STUDIES GUIDE

FOR PATIENTS ≤ 10KG

Correlative Study	Appx	Sample volume				Tube Type
		Volume per sample	Total Cycle 1	Total Cycle 2	Subsequent Cycles	
Pharmacokinetic Study	IX	2.5-3.5ml	11ml	6ml	Included with Immunogenicity Samples	SST Tubes
Immunogenicity Study (Anti-Drug Antibody)	X	3.5ml	0ml	0ml	3.5ml	SST Tubes
Pharmacodynamics- T lymphocyte saturation/cellular SEMA4D assay	VI	4ml	20ml	4ml	4ml	Cyto-Chex Tubes
Pharmacodynamics- Total Soluble SEMA4D	XI	3.5ml	0ml	0ml	3.5ml	SST Tubes
Total Blood Volume			31ml	10ml	11ml	

FOR PATIENTS > 10KG

Correlative Study	Appx	Sample volume				Tube Type
		Volume per sample	Total Cycle 1	Total Cycle 2	Subsequent Cycles	
Pharmacokinetic Study	IV	2.5ml	12.5ml	7.5ml	Included with Immunogenicity Samples	SST Tubes
Immunogenicity Study (Anti-Drug Antibody)	V	3.5ml	7ml	3.5ml	3.5ml	SST Tubes
Pharmacodynamics- T lymphocyte saturation/cellular SEMA4D assay	VI	4ml	20ml	4ml	4ml	Cyto-Chex Tubes
Pharmacodynamics- Total Soluble SEMA4D	VII	3.5ml	7ml	3.5ml	3.5ml	SST Tubes
Total Blood Volume			46.5ml	18.5ml	11ml	

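### Patients of 10 kg or less have no baseline or Cycle 2 anti-drug antibody test in the detailed schedule, which conflicts with Section 8.1, although 3.5 ml is already drawn at both visits

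*Combined protocol and SAP*

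**What the plan says.** **Antibody sampling, 10 kg or less.** Section 8.4.2(a) lists only "Cycle 3, Day 1 and each subsequent cycle, Day 1: prior to start of infusion". Appendix II agrees: its immunogenicity row for these patients reads "X 3.5ml 0ml 0ml 3.5ml" (form number, volume per sample, Cycle 1, Cycle 2, each later cycle). The Appendix X form has rows from Cycle 3 only.

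**Antibody sampling, over 10 kg.** Section 8.4.2(b) starts with "Cycle 1, Day 1: prior to start of infusion and at the end of infusion" and continues before dosing on Day 1 of every later cycle.

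**Pharmacokinetic sampling, 10 kg or less.** Section 8.3.2(a) has "Cycle 1, Day 1: prior to start of infusion [3.5 ml], at the end of infusion [2.5 ml" and, later, "Cycle 2, Day 1: prior to start of infusion [3.5 ml". The other Cycle 1 and Cycle 2 draws are 2.5 ml. Appendix IX repeats these volumes and states joint use with immunogenicity only for cycles after Cycle 2.

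**What 3.5 ml stands for.** Section 8.3.3: "For blood samples that are to be used for both pharmacokinetic analysis and immunogenicity analysis, 3.5 ml of blood will be drawn total".

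**Summary schedule.** In the Section 8.1 table, the row "Immunogenicity Study" has an X under Pre-Study with no weight limit and no footnote. Footnote 9, which defers to Section 8.4, is attached only to the Cycle 1 and later-cycle cells.

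**Aim served.** Secondary aim 1.2.2, the immunogenicity of VX15/2503 in pediatric patients.

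**The concern.** An antibody result is read against a pre-dose sample. Without one, a positive result could reflect reactivity that was there before treatment or a response to the drug. In the lightest children the detailed schedule omits that sample, while the summary schedule appears to require it. A site enrolling such a child therefore has two incompatible instructions for a study headed as required.

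Section 8.4.2 also has no end-of-treatment antibody sample. By contrast, the T-lymphocyte saturation schedule in Section 8.5.2 has a Day 28 draw whether or not the patient goes on to Cycle 2. A small child who stops during the first two cycles therefore contributes nothing to aim 1.2.2.

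The usual reason for thinning a schedule in small children is blood volume. That reason does not explain this gap, because the pre-dose draws at both visits are already the size the protocol specifies for a shared sample.

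**Working it through.** **Step 1. Timing of the first antibody sample.** Cycles last 28 days, with infusions on Days 1 and 15 (Section 5.1).

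- Cycle 3 Day 1 = 2 × 28 + 1 = day 57, which is 56 days after the first dose.
- Infusions already given = 2 cycles × 2 = 4.

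**Step 2. Reproduce the Appendix II totals for patients of 10 kg or less.** Inputs are the volumes in Sections 8.3.2(a), 8.4.2(a), 8.5.3 and 8.6.2.

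| | PK | T-cell saturation | Antibody | Soluble SEMA4D | Total |
|---|---|---|---|---|---|
| Cycle 1 | 3.5 + 2.5 + 2.5 + 2.5 = 11 ml | 5 × 4 = 20 ml | 0 | 0 | 31 ml |
| Cycle 2 | 3.5 + 2.5 = 6 ml | 4 ml | 0 | 0 | 10 ml |
| Cycle 3 onwards | shared with antibody sample | 4 ml | 3.5 ml | 3.5 ml | 11 ml |

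These match the stated 31, 10 and 11 ml. The totals for patients over 10 kg (46.5, 18.5 and 11 ml) also reproduce.

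**Step 3. Is the shared-sample volume already counted?** Compare three ways of handling the two pre-dose visits.

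| Handling of Cycle 1 Day 1 and Cycle 2 Day 1 pre-dose | Cycle 1 | Cycle 2 |
|---|---|---|
| PK only, at 2.5 ml each | 31 − 1 = 30 ml | 10 − 1 = 9 ml |
| As published, 3.5 ml each | 31 ml | 10 ml |
| As published, plus a separate 3.5 ml antibody tube | 34.5 ml | 13.5 ml |

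The published totals already carry an extra 1 ml at each visit. Testing antibodies on the existing draws adds no blood. Both analyses use SST tubes and go to the same central laboratory.

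**Step 4. What the schedule as written can and cannot show.**

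- Positive at Cycle 3 Day 1: cannot be classed as pre-existing or treatment-induced.
- A response that appears and disappears before Cycle 3: missed.
- Negative at Cycle 3 Day 1 and positive later: conversion on treatment is visible, subject to the assay's tolerance to circulating drug, which the documents do not give.
- Off therapy before Cycle 3: no antibody data.

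**Step 5. How many small children might leave before Cycle 3 (illustration only).** The documents give no pediatric figure. Section 2.3.1 reports for adults that 45.2% had stable disease for at least 8 weeks (56 days). It also gives a progression-free survival of 7.82 weeks, without calling it a median. If that figure is taken as a median with exponential progression (assumption):

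- 7.82 × 7 = 54.7 days
- exp(−ln 2 × 56 / 54.7) ≈ 0.49

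Both routes suggest that roughly half would still be on therapy at Cycle 3 Day 1. The data come from adults with mixed tumors on weekly dosing, so this indicates scale and is not an estimate for this trial.

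**The case against.** The best defense is that the reduced schedule is deliberate and that a specific section outranks a summary table. Sections 8.4.2(a) and Appendices II and X agree with one another. Soluble SEMA4D is likewise not sampled in Cycles 1 and 2 in these patients, which looks like planned blood sparing. The X in Section 8.1 may simply be generic. The two 3.5 ml draws are labelled pharmacokinetic, and the lab manual, which is not available here, may use the extra millilitre. The aim is secondary, Section 11.5 calls the correlative analyses descriptive, and with a minimum age of 12 months very few children, perhaps none, will weigh 10 kg or less.

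Much of this stands. That the 3.5 ml draws were meant for joint use is an inference from Section 8.3.3, not something the protocol states, and the impact is small. What does not stand is blood sparing as a reason for omitting the antibody test, since the shared-sample volume is drawn anyway. Nor is the conflict removed by preferring the detailed section: the Pre-Study cell lacks the footnote that sends the reader to Section 8.4.

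Two stronger readings are tempting and not supported. A reader might infer that treatment-induced antibodies cannot be identified in these children at all. Sampling on Day 1 of every cycle from Cycle 3 still allows later conversion to be seen. A reader might also infer that the gap falls on the very group the pharmacokinetic expansion was added to study. Section 11.1 aims that expansion at patients under 12 years, and Section 2.5 opens it from 12 months to 21 years. Children of 10 kg or less are only its lightest part.

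**Conclusion.** The point holds as an internal inconsistency with a limited scientific cost. For patients of 10 kg or less, Section 8.4.2(a) and Appendices II and X omit the baseline and Cycle 2 antibody tests, in conflict with the unrestricted Pre-Study mark in Section 8.1. If the detailed schedule is followed, the first result comes on day 57, after four infusions. An antibody found then cannot be attributed to treatment or to a pre-existing state, and early leavers provide no data.

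The number affected is probably small, which is an assumption because the documents give no expected count. The proportion lost before Cycle 3 could be about half if adult experience carried over, but that would be half of a handful. No primary endpoint or decision rule depends on it. This is a low-priority correction, worth making because it is nearly free.

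The schedule and volumes are certain from the text. Whether the 3.5 ml draws were intended for both analyses is not.

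**What to change.** Reconcile Sections 8.1, 8.3.2(a) and 8.4.2(a) and Appendices II, IX and X:

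- In Section 8.4.2(a) and Appendix X, add Cycle 1 Day 1 and Cycle 2 Day 1 pre-infusion as antibody time points, taken from the 3.5 ml samples already drawn.
- In Section 8.3.2(a) and Appendix IX, state that these two samples serve both analyses, as is done for patients over 10 kg.
- In Appendix II, show the shared samples under immunogenicity, the convention used in the table for patients over 10 kg. Cycle 1 becomes 7.5 (PK) + 3.5 (antibody) + 20 (T-cell) = 31 ml, and Cycle 2 becomes 2.5 + 3.5 + 4 = 10 ml.
- In Section 8.1, attach footnote 9 to the Pre-Study cell as well.

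If the sponsor instead intends no early antibody test in these children, the Pre-Study mark should be restricted by weight, the use of the extra 1 ml explained, and the report should say that antibodies present at Cycle 3 Day 1 are of unknown origin.

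The recommended change costs wording edits and two assays per small child (one if the child stops before Cycle 2). Blood totals are unchanged, provided the lab manual does not commit the extra 1 ml to another use; check that first.

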8.4.3 Sample Collection and Handling Instructions

Please refer to the lab manual. Briefly, blood samples (3.5 ml) will be collected in SST tubes at a site distant from the infusion for both immunogenicity evaluation and pharmacokinetic evaluation. Record the exact time that the sample is drawn along with the exact time that the drug is administered.

8.4.4 Sample Processing

Please refer to lab manual

8.4.5 Sample Labeling

Each tube must be labeled with the patient's study registration number, the study I.D., and the date and time the sample was drawn. Data should be recorded on the Correlative Study Form, which must accompany the sample(s). Please refer to the Covance lab manual for additional information.

8.4.6 Sample Shipping Instructions

Samples should be shipped to the following address:
Covance Central Laboratory Services, Inc.
[name]
[name]

8.5 **Pharmacodynamics: T-lymphocyte saturation (Required)**

8.5.1 Description of Studies

Blood samples will be evaluated for T-lymphocyte saturation by VX15/2503 utilizing a validated flow-cytometry based assay.

8.5.2 Sampling Schedule (See [Appendix VI](#))

- c) For all patients, samples will be collected at:
 - Cycle 1, Day 1: prior to start of infusion and at the end of infusion
 - Cycle 1, Day 15: prior to start of infusion and at the end of infusion
 - Cycle 1, Day 28: prior to Cycle 2, Day 1 dose for all patients regardless of whether or not patient is proceeding to Cycle 2

THIS PROTOCOL IS FOR RESEARCH PURPOSES ONLY, SEE PAGE 1 FOR USAGE POLICY

- Each subsequent cycle, Day 1: prior to start of infusion

8.5.3 Sample Collection and Handling Instructions

Blood samples:

- Cycle 1 Day 1: 2 x 4mL
- Cycle 1 Day 15: 2 x 4mL
- Cycle 1 Day 28: 1 x 4mL
- Subsequent Cycles: prior to start of infusion, Day 1: 1 x 4mL

Blood samples will be collected in cyto-chex tubes at a site distant from the infusion for pharmacodynamic evaluation. Record the exact time that the sample is drawn along with the exact time that the drug is administered.

8.5.4 Sample Processing

Please refer to lab manual

8.5.5 Sample Labeling

Each tube must be labeled with the patient's study registration number, the study I.D., and the date and time the sample was drawn. Data should be recorded on the Correlative Study Form, which must accompany the sample(s). Please refer to the Covance lab manual for additional information.

